2.3 Clinical Studies in Adults

2.3.1 Phase 1 Clinical Trial

Flotetuzumab monotherapy is currently under clinical investigation in adults with relapsed or refractory AML (rrAML) after treatment failure via the phase 1 trial CP-MGD006-01 (NCT02152956; MacroGenics). This trial was planned to evaluate up to 10 dose levels and/or schedules of flotetuzumab monotherapy. In this study, a maximally tolerated dose (MTD) and recommended Phase 2 dose (RP2D) was defined as 500 nanograms/kg/day administered continuously for a 28 day cycle.³⁰ Dose-limiting toxicity of grade 3 IRR/CRS occurred in 3 of 9 adults (n=1 each for CRS, syncope, and arthralgia/myalgia) treated at 700 nanograms/kg/day. Data from the CP-MGD006-01 trial demonstrate tolerability of flotetuzumab with a step-up dose regimen, which utilizes lower-dose flotetuzumab at initiation followed by a two-stage intra-patient escalation during the first week and continuous dosing at the MTD for the following 21 days. This approach has minimized infusion-related reactions (IRR)/CRS while preserving anti-leukemia activity. The study initially explored an intermittent dosing schedule (4 days on/3 days off) but, due to safety and efficacy concerns, the trial has subsequently been amended to treat all patients with continuous 28-day infusions. At the cut-off date on November 1, 2018, 31 patients have been treated at the RP2D. Anti-leukemic activity was reported in 18/27 (67%) response-evaluable patients, with an overall response rate (CR/CRI/MLF [morphologic leukemia free state]/PR) of 26% (6/27) and a CR/CRI rate of 19% (5/27). Interestingly, all 5 of the patients who had a CR/CRI were considered primary chemotherapy-refractory patients (defined as refractory to ≥ 2 induction attempts, or first CR with initial CR < 6 months) compared to none of the patients with relapsed AML.³¹

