8.2 Pharmacology (Required)

8.2.1 Description of Studies and Assay

Pharmacokinetics (PK) will be performed to determine the PK of flotetuzumab in children. Serum samples will be collected and flotetuzumab concentration will be determined by a validated electrochemiluminescent (ECL)-based sandwich assay. Samples will be analyzed by MacroGenics Pharmaceuticals. Bioanalytical measures will be combined with respective individual patient dosing history and demographic information. Pharmacometric analysis will be performed using an appropriate model-based approach. PK parameters will be correlated with toxicity parameters. PK exposures will be compared between patients who achieve CR/CRi and those who do not.

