8.3 Immunogenicity Study (Required)

8.3.1 Description of Studies and Assay

Serum samples will be collected and anti-flotetuzumab antibodies will be detected using a validated bridging immunoassay by a MacroGenics, Inc. bioanalytical lab. Immunogenicity will be compared between patients who achieve CR/CRi and those who do not.

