11.5 Pharmacokinetic and Correlative Studies and Response Analysis

A descriptive analysis of pharmacokinetic (PK) parameters of flotetuzumab will be performed to define systemic exposure, drug clearance, and other pharmacokinetic parameters. The PK parameters will be summarized with simple summary statistics, including means, medians, ranges, and standard deviations (if numbers and distribution permit).

While the primary aim of this study is to evaluate the toxicity of flotetuzumab, patients will have disease evaluations performed as indicated in [Section 8.1](#). Disease response will be assessed according to the revised AML International Working Group (IWG) criteria³⁷ and will be reported descriptively.

CD123 expression will be analyzed in an exploratory fashion, both using a binary scale and using a continuous scale to evaluate whether there are correlations between CD123 expression and antitumor effects. Anti-drug antibody analyses will be measured by MacroGenics. Biomarkers, including those identified in the secondary objectives, will be evaluated for association with cytogenetic/molecular features and outcome.

All these analyses will be descriptive and exploratory and hypothesis-generating in nature.

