12.2.4 Partial Response (PR)

A decrease of at least 50% in the percentage of blasts to 5% to 25% in the bone marrow aspirate. Bone marrow must have adequate cellularity (e.g., > 15%) to determine response. PR status will not be included in calculation of response to the regimen. A repeat bone marrow aspiration after several weeks may be required to distinguish between a PR and increased blasts caused by bone marrow regeneration. A value of < 5% blasts may also be considered a PR if Auer rods are present.

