12.2.6 Stable Disease (SD)

Criteria for CR, CRp, CRI, CRc, PR, or progressive disease (PD) not met.

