- b. Physical exam (including VS). Prior to subsequent cycles.
- c. CBC/diff/platelets. Weekly. If patients develop Grade 4 neutropenia then CBCs should be checked at least every 3 to 4 days until recovery to Grade 3 or until meeting the criteria for dose limiting toxicity.
- d. Ht/Wt/BSA. Prior to subsequent cycles.
- e. Electrolytes including Ca⁺⁺. Prior to subsequent cycles.
- f. Creatinine, ALT, bilirubin, and AST. Prior to subsequent cycles.
- g. Albumin. Prior to subsequent cycles.
- h. Imaging (CT or MRI) of chloroma. Only to be performed if clinically indicated. At the end of every cycle (if present on previous study).
- i. ECHO or gated radionuclide study. Prior to subsequent cycles.
- j. EKG. Prior to subsequent cycles.
- k. Neurologic exam. Prior to subsequent cycles.
- l. CD3 T-lymphocyte quantification. In consenting patients, samples to be collected on Day 1 of Cycles 2+. See [Section 8.6](#) for details.
- m. Cytokine production measurement. If patients experience IRR/CRS, blood samples are to be collected from consenting patients at the time of IRR/CRS and at the time of IRR/CRS resolution (if applicable). See [Section 8.7](#) for details.
- n. Bone marrow aspirate. At the end of every cycle.
- o. Immunogenicity study. Samples to be collected from all patients on Cycle 3, Day 1 (pre-infusion), and on Cycle 5, Day 1 (pre-infusion). See [Section 8.3](#) for details.
- p. Pharmacokinetics. Blood samples will be collected 30 minutes, 1 hour, 2 hours, 4 hours, 8 hours, and 24 hours after the end of infusion on the patient's last day of

THIS PROTOCOL IS FOR RESEARCH PURPOSES ONLY, SEE PAGE 1 FOR USAGE POLICY

protocol therapy. See [Section 8.2](#) for details.

- q. NGS MRD comparison with flow cytometry MRD. In consenting patients only at the time of bone marrow evaluation. See [Section 8.5](#) for details.
- r. Flow cytometry with MRD determination. At the end of each cycle with bone marrow evaluation.

This listing only includes evaluations necessary to answer the primary and secondary aims. OBTAIN OTHER STUDIES AS REQUIRED FOR GOOD CLINICAL CARE.

Comments

(Include any held doses, or dose modifications)

THIS PROTOCOL IS FOR RESEARCH PURPOSES ONLY, SEE PAGE 1 FOR USAGE POLICY

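### Section 8.2.1 compares drug exposure only between CR/CRi and all other patients; an ordered and a continuous marrow response should be added as exploratory analyses

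*Combined protocol and SAP*

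**What the plan says.** On exposure and response, Section 8.2.1 states: "PK exposures will be compared between patients who achieve CR/CRi and those who do not". No section plans a graded or continuous response against exposure. Section 11.5 promises summary statistics for the PK parameters and a descriptive report of disease response, and adds: "All these analyses will be descriptive and exploratory and hypothesis-generating in nature".

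The response data are richer than two groups. Section 8.1 schedules a marrow before the study and at the end of Cycle 1, and Appendix V continues: "Bone marrow aspirate. At the end of every cycle". Section 12.2 defines CR, CRp, CRi, PR, SD and PD. PR is itself a measured change: "A decrease of at least 50% in the percentage of blasts to 5% to 25% in the bone marrow aspirate". SD is whatever remains: "Criteria for CR, CRp, CRI, CRc, PR, or progressive disease (PD) not met". CRp (12.2.2) is defined separately from CRi (12.2.3).

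For one predictor the plan does keep the full scale: "CD123 expression will be analyzed in an exploratory fashion, both using a binary scale and using a continuous scale" (Section 11.5). It does not do so for response in the PK analysis.

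**The concern.** The contrast places a patient whose blasts fell by half in the same group as a patient who progressed. If exposure matters, part of its effect will appear as differences within that group, where this comparison cannot see it.

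The adult data in Section 2.3.1 suggest how often this could happen. CR/CRi was 5/27, while "Anti-leukemic activity was reported in 18/27 (67%) response-evaluable patients". Thus 13 of the 22 adults outside CR/CRi (59%) had some activity.

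What is at stake is how precisely the trial can describe the link between exposure and anti-leukemic effect. Every patient gives Cycle 1 PK samples and should have repeated marrows, so the fuller comparison uses data already collected. It would also serve secondary aim 1.2.2, the preliminary look at anti-tumor activity.

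**Working it through.** **Planned size.** Section 11.1 gives up to 18 evaluable patients for dose finding, up to 6 more for PK, and 10% attrition: (18 + 6)/0.9 = 26.7, rounded up to 27, which matches the plan. The absolute maximum also reproduces: (36 + 6)/0.9 = 46.7, rounded up to 47. The check below uses 24 patients. The plan states no alpha, power or effect size for the exposure comparison.

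**Size of the remission group.** At the adult rate of 5/27:
- expected remissions are 24 × 5/27 = 4.4, or 18 × 5/27 = 3.3 with dose-finding patients only;
- the binomial chance of 2 or fewer among 24 is 15%, and of 1 or fewer among 18 is 13%.

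**Information kept.** Assume a normal latent response. With φ the normal density and z the cut-point, splitting off the top share p keeps φ(z)²/[p(1 − p)] of the information in the continuous response.
- For p = 5/27, z = 0.896 and φ = 0.267, so 0.0713/(0.185 × 0.815) = 0.47. The figure is 0.34 if the CR/CRi rate is 10% and 0.59 if it is 33%.
- For ordered categories, sum (difference in φ at the two boundaries)²/share. Assume shares of PD 9/27, SD 12/27, PR 1/27 and CR/CRi 5/27, with φ at the boundaries 0.364, 0.298 and 0.267. The sum is 0.397 + 0.010 + 0.026 + 0.385 = 0.82.
- The split therefore keeps 0.47/0.82 = 58% of what four categories hold.
- With three levels only (CR/CRi, PR, all others) the figure is 0.53. Most of the gain comes from separating SD from PD.

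The PR share takes 6/27 for overall response. Section 2.3.1 prints that as 26%, which is 7/27; 6/27 is 22%. Using 7/27 gives 0.83 for four categories and 0.57 for three.

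**Illustrative power.** Exposure and latent response were simulated as bivariate normal with correlation rho, 24 patients, two-sided 5%, and the four categories above.

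| rho | Split, exact Mann-Whitney | Split, t-test | Four ordered categories (Kendall) | Continuous (Spearman) |
|---|---|---|---|---|
| 0.4 | 21% | 26% | 39% | 45% |
| 0.5 | 34% | 38% | 59% | 65% |
| 0.6 | 48% | 53% | 79% | 85% |

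At rho 0.3 everything is weak: 13% to 16% for the split and 23% to 24% for four categories. At rho 0.2, the exact test on the split gives 9% and four categories 12%.

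**Sensitivity to the SD/PD boundary (rho 0.5).** The base case treats the 18/27 adults with activity as SD or better. Moving that share to 35% or 85% puts the four-category figure at 50% to 58%. Removing the boundary, which leaves CR/CRi, PR and all others, gives 38% to 39%, no better than the t-test on the split.

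**The case against.** The strongest reply is that Section 11.5 makes all of this descriptive and hypothesis-generating. No test is planned, so no power is lost against a stated aim, and nothing stops the team plotting exposure by response category. This stands as a limit on the point. The power figures only show how much information each scale carries. A descriptive difference between about 4 and 20 patients is imprecise for the same reason, and naming the scale in advance avoids choosing it after the data are seen.

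A second reply is that the cut is deliberate: Section 12.2.4 leaves PR out of the calculation of response to the regimen. That governs the response rate and need not set the scale for relating exposure to effect. Elsewhere the protocol treats PR as decisive, since patients without at least a PR after Cycle 2 stop treatment (5.1, 5.2, 10.1).

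A third reply is that the gain rests on unsupported inputs. This stands in part. The documents give no value for rho, and Section 2.3.1 does not define anti-leukemic activity in terms of SD and PD here. Some of the gap also reflects the conservatism of the exact test, which is why the t-test is shown beside it.

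Two stronger readings are tempting, and the documents do not support them.
- A reader might infer that the dichotomy could distort dose selection. The choice between 500 and 700 nanograms/kg/day follows DLT counts (5.1, 11.1, 11.3), and the possible amendment to 900 depends on clearance (5.3.1). Neither uses the exposure-response comparison.
- A reader might extend the point to immunogenicity, because Section 8.3.1 uses the same contrast: "Immunogenicity will be compared between patients who achieve CR/CRi and those who do not". Post-baseline ADA samples are scheduled only at Cycle 3 and Cycle 5 Day 1 (8.3.2), and reaching Cycle 3 mostly requires at least a PR. Apart from patients who start Cycle 3 with results pending or have unscheduled samples, those with SD or PD give only a baseline sample. Grading response would recover little there; the sampling schedule is the limit.

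**Conclusion.** The point holds for the PK comparison in Section 8.2.1, as a loss of descriptive precision. At the adult CR/CRi rate the stated contrast rests on about 4 remissions among 24 patients. It keeps about 47% of the information in a continuous response and 58% of that in four ordered categories.

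The percentages assume a normal latent response, adult response rates carried over to children, and a boundary between SD and PD that the documents do not supply. The advantage of grading is clear for rho of 0.4 to 0.6 and small in absolute terms below that. It nearly disappears if PR is separated but SD and PD stay together.

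This is worth changing because the better analysis costs almost nothing. It does not put the primary aims, the dose decision or the ADA analysis in doubt.

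**What to change.** In Sections 8.2.1 and 11.5, keep CR/CRi versus not as a display and add two analyses, labelled exploratory and reported as estimates with confidence intervals:

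1. Exposure against ordered best response, CR/CRp/CRi > PR > SD > PD, with SD kept separate from PD, for example by Kendall's tau or a proportional-odds model. This also settles where CRp belongs.
2. Exposure against best percent change from baseline in marrow blasts, among patients with evaluable marrows, by Spearman correlation with a scatter plot.

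The cost is a few sentences and a little more analysis, with no new samples, visits or patients. The second analysis loses patients with aplastic or severely hypocellular marrows, which Section 12.2.8 calls unevaluable. The documents do not say how many to expect, so that number should be reported with the result.

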8.2.2 Sampling Schedule (See [Appendix VI-A](#), [Appendix VI-B](#), and [Appendix VI-C](#))

The PK sampling schedule will vary according to the dose level assignment of the patient. For all patients being treated on DL1, blood samples will be collected at the following time points*:

- Cycle 1, Day 1: prior to start of infusion
- Cycle 1, Days 3 – 7: 30 minutes prior to syringe change and dose escalation

THIS PROTOCOL IS FOR RESEARCH PURPOSES ONLY, SEE PAGE 1 FOR USAGE POLICY

- Cycle 1, Day 8: 24 hours after Day 7 syringe change and final dose escalation
- Cycle 1, Day 12, Day 15, Day 19, Day 22, Day 27, and Day 29 (prior to infusion ending): any time

For all patients being treated on DL-1, blood samples will be collected at the following time points*:

- Cycle 1, Day 1: prior to start of infusion
- Cycle 1, Day 4, Day 6, and Day 8: 30 minutes prior to syringe change and dose escalation
- Cycle 1, Day 9: 24 hours after Day 8 syringe change and final dose escalation
- Cycle 1, Day 13, Day 17, Day 21, Day 25, and Day 29 (prior to infusion ending): any time

For all patients being treated on DL2, blood samples will be collected at the following time points*:

- Cycle 1, Day 1: prior to start of infusion
- Cycle 1, Days 3 – 8: 30 minutes prior to syringe change and dose escalation
- Cycle 1, Day 9: 24 hours after Day 8 syringe change and final dose escalation
- Cycle 1, Day 13, Day 17, Day 21, Day 25, and Day 29 (prior to infusion ending): any time

*All time points given are for patients that follow the dosing schedule exactly as outlined in [Section 5.1](#). For patients that require dose interruptions during Cycle 1, PK samples should be drawn according to when the patient reaches certain dose levels (see [Appendix VI-A](#), [Appendix VI-B](#), and [Appendix VI-C](#) for details).

Blood samples will also be collected at the following time points on the patient's last day of protocol therapy:

- 30 minutes, 1 hour, 2 hours, 4 hours, 8 hours, and 24 hours after the end of infusion

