2.5 Overview of Proposed Pediatric Study

This is a Phase 1 study using a rolling six design³⁵ with one potential dose escalation cohort. The primary aim of the study is to identify safe and tolerable dosing of the CD123 x CD3 DART flotetuzumab in children < 21 years of age with AML in second or greater relapse, refractory AML after two or more chemotherapy cycles, first relapse after primary chemotherapy-refractory disease, or first relapse after hematopoietic stem cell transplantation (HSCT).

Flotetuzumab will be administered continuously for a total of 28 days (**NOTE:** infusion ends on Day 29). Step-up dosing will be used in the first 7 days of Cycle 1 to minimize

THIS PROTOCOL IS FOR RESEARCH PURPOSES ONLY, SEE PAGE 1 FOR USAGE POLICY

IRR/CRS, followed by 21 days at the adult recommended phase 2 dose (RP2D) (500 nanograms/kg/day; dose level 1, [DL1]).³¹ If DL1 is safe and tolerable based on standard immunotherapy DLT assessments²⁷, an additional cohort of patients will dose-escalate flotetuzumab to 700 nanograms/kg/day (DL2). If fewer than 2 DLTs occur at DL2, this will be considered the RP2D. If there are ≥ 2 DLTs at DL2, DL1 will be considered the MTD of flotetuzumab monotherapy. If flotetuzumab monotherapy at DL1 is not tolerable, dose de-escalation will occur to 300 nanograms/kg/day (DL-1). If DL-1 is deemed tolerable, this dosing will be the MTD. Further dose de-escalation beyond DL-1 will not be permitted and will limit further exploration of flotetuzumab in this patient population.

Bone marrow evaluation will be performed on Day 29 (+/- 1 day) as an exploratory measurement of response. Following the end of flotetuzumab infusion on Day 29, patients will be allowed a treatment-free interval of up to 3 days to allow treatment respite. The duration of this treatment-free interval will be up to the treating physician's discretion. However, patients may also skip the treatment-free interval and proceed immediately to the next cycle of therapy while awaiting results from response evaluation.

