9.3 Useful Links and Contacts

- CTEP Forms, Templates, Documents:
<http://ctep.cancer.gov/forms/>
- NCI CTEP Investigator Registration:
[contact]
- CTEP Identity and Access Management (IAM) account:
<https://ctepcore.nci.nih.gov/iam/>
- CTEP Associate Registration and IAM account help:
[contact]
- IB Coordinator:
[contact]

10.0 CRITERIA FOR REMOVAL FROM PROTOCOL THERAPY AND OFF STUDY CRITERIA**10.1 Criteria for Removal from Protocol Therapy**

- a) Clinical (including physical examination or serum tumor markers) or radiographic

THIS PROTOCOL IS FOR RESEARCH PURPOSES ONLY, SEE PAGE 1 FOR USAGE POLICY

evidence of progressive disease (See [Section 12](#)).

- b) Have not achieved at least a PR following 2 successive treatment cycles.
- c) Adverse Events requiring removal from protocol therapy (See [Section 13](#)).
- d) Development of a DLT following 1 dose reduction.
- e) An infusion stop or delay of more than 2 weeks due to AE or more than 2 discontinuations per cycle due to AE (does not apply for prolongation of the scheduled treatment free period of a cycle).
- f) Refusal of protocol therapy by patient/parent/guardian
- g) Non-compliance that in the opinion of the investigator does not allow for ongoing participation.
- h) Completion of 6 cycles of therapy.
- i) Physician determines it is not in the patient's best interest.
- j) Repeated eligibility laboratory studies (CBC with differential, bilirubin, ALT (SGPT) or serum creatinine) are outside the parameters required for eligibility prior to the start of flotetuzumab (See [Section 8.1](#)).
- k) Study is terminated by Sponsor.
- l) Pregnancy

Patients who are removed from protocol therapy during Cycle 1 should continue to have the required observations in [Section 8.1](#) until the originally planned end of the cycle or until all adverse events have resolved per [Section 13.4.4](#), whichever happens LATER. The only exception is with documentation of the patient's withdrawal of consent. Patients who are removed from protocol therapy in subsequent cycles should have the necessary observations to ensure adequate clinical care.

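### The only post-infusion PK series is tied to a last day of therapy that may be recognised only afterwards, so it can be lost in patients whose therapy is ended during a break

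*Combined protocol and SAP*

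**What the plan says.** Section 8.2.2 lists the Cycle 1 samples by dose level. They are one pre-dose draw, then draws during the infusion, ending with "Day 29 (prior to infusion ending): any time". It then adds a separate series: "Blood samples will also be collected at the following time points on the patient's last day of protocol therapy", at "30 minutes, 1 hour, 2 hours, 4 hours, 8 hours, and 24 hours after the end of infusion". Footnote 1 to the Section 8.1 table, code e in the Cycle 1 therapy delivery maps and code p in the Cycles 2+ map repeat the same condition. Each PK form (Appendix VI-A to VI-C) has a single block for this series, with the cycle number left blank.

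On timing, Section 2.5 says "Bone marrow evaluation will be performed on Day 29 (+/- 1 day) as an exploratory measurement of response". After the infusion ends on Day 29, "patients will be allowed a treatment-free interval of up to 3 days to allow treatment respite". The plan accepts that the marrow result may not be back by then: "patients may also skip the treatment-free interval and proceed immediately to the next cycle of therapy while awaiting results from response evaluation". Section 5.2 makes the same allowance.

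Therapy ends on progressive disease at any time (Sections 2.5 and 5.2) and, under Section 10.1, for patients who "Have not achieved at least a PR following 2 successive treatment cycles". Section 12.2 also expects that some patients in morphologic remission will leave for transplant.

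**The concern.** The sampling rule requires the site to know, when the pump is switched off, that this is the final infusion. For a patient on a break with the marrow result outstanding, nobody knows that yet. If the result or another decision then ends therapy, the infusion that turned out to be the last is hours or days in the past. No passage tells sites to draw the series in advance when continuation is open, and none gives a fallback.

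The data at stake are those that describe the fall in concentration after the infusion stops. Secondary aim 1.2.1 is to characterise the pharmacokinetics in children, and Section 11.5 promises exposure, clearance and other parameters. Half-life and volume of distribution depend largely on this series. Numbers are small: at most 18 evaluable patients for the MTD/RP2D, plus up to 6 enrolled to acquire PK data in young patients (Section 11.1). Each lost series therefore matters.

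**Working it through.** **1. The plan's own PK blood volume (Appendix II: 20 to 57 ml).** Inputs are the sample counts in Section 8.2.2 and 2 to 3 ml per sample.

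| Dose level | Cycle 1 samples | With the 6 post-infusion samples |
|---|---|---|
| DL1 | 1 + 5 + 1 + 6 = 13 | 19 |
| DL-1 | 1 + 3 + 1 + 5 = 10 | 16 |
| DL2 | 1 + 6 + 1 + 5 = 13 | 19 |

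- Upper bound: 19 × 3 ml = 57 ml. This matches Appendix II and allows exactly one post-infusion series.
- Lower bound: 10 × 2 ml = 20 ml. This also matches, and allows no post-infusion series. With one full series the minimum would be 16 × 2 = 32 ml.

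The stated budget therefore fits at most one series per patient, not one at every Day 29.

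**2. Whether the last day is known in time.**

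| Situation | End of infusion recognised as final at the time? |
|---|---|
| Stopped during an infusion (toxicity, overt progression, refusal) | Yes |
| Goes straight into the next cycle and is stopped while on infusion | Yes |
| Completes Cycle 6 | Yes |
| On a break, then stopped on the pending marrow result | Not necessarily |
| On a break, then leaves for transplant or another reason | Not necessarily |

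Only the last two rows are exposed. A stop for less than PR arises after Cycle 2, when the patient may be an outpatient (Section 5.1). After Cycle 1, the response-based stop is progression.

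**3. Whether a missed series can be recovered.** Percent of drug remaining t hours after the infusion ends = 100 × 2^(−t / half-life), assuming first-order decline. Section 2.2.3 gives 3.5 h in monkeys; no human value is given. The 2 h and 7 h rows are an assumed range.

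| Half-life | 0.5 h | 1 h | 2 h | 4 h | 8 h | 24 h |
|---|---|---|---|---|---|---|
| 2 h | 84% | 71% | 50% | 25% | 6% | 0.02% |
| 3.5 h | 91% | 82% | 67% | 45% | 21% | 0.86% |
| 7 h | 95% | 91% | 82% | 67% | 45% | 9.3% |

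A decision taken a day or more into the break forfeits the 0.5 to 8 h samples, and a 24 h sample alone does not define the decline.

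**4. Whether the Cycle 1 samples substitute.** The step-up samples come about 24 h after the previous rate change (DL1, DL2) or about 48 h after it (DL-1). At 3.5 h, 24 h is 24 / 3.5 = 6.9 half-lives, so concentrations are 100 − 0.86 = 99% of the way to the new plateau. At the assumed 7 h they are 100 − 9.3 = 91% of the way. These samples inform clearance and exposure well, and half-life and volume poorly.

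**5. Share of patients affected.** This would be the chance of being on a break at a given infusion end, times the chance that therapy is ended during that break, times the chance that the site has not drawn the series anyway. The documents give none of the three: no marrow turnaround time, no break uptake, and no expected stopping rate for this trial.

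**The case against.** The strongest reply is that the gap is narrow and the consequence modest. The marrow may be done on Day 28, so a result could arrive before the infusion ends. A careful site may draw the series whenever continuation is in doubt. The therapy maps do prompt sites: code e appears on Day 29 of the Cycle 1 maps and code p on Day 29 of the Cycles 2+ map. Section 8.2.1 specifies a model-based analysis, which does not need a full series in every patient. The planned comparison by CR/CRi is of exposures, which the Cycle 1 samples support.

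Most of this stands and limits the point to data that can be lost, not data that will be. It does not close the gap. Codes e and p carry the same last-day condition, so a site following them literally has no reason to draw at an undecided infusion end. A model can borrow only from patients in whom the series was drawn.

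Two stronger readings are tempting and are not supported:

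- A reader might take adult non-response as the loss rate. Section 2.3.1 prints 26% beside 6/27, so non-response is either about 74% (20/27) or 78% (21/27), and one might infer that three quarters of patients lose the series. That would require every non-responder to be on a break, none to stop mid-infusion, every result to arrive too late, and no site to sample ahead.
- A reader might infer that the loss falls on non-responders. Responders who leave for transplant after a break are exposed in the same way, and non-responders stopped on infusion are captured. The direction of any selection is unknown.

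**Conclusion.** The point holds as a gap in the sampling schedule that is worth closing. Following the rule as written can permanently lose six of 19 PK samples (six of 16 at DL-1) in a patient whose therapy is ended during a break, and those six are the only elimination-phase data. The conclusion rests on reading the last day of therapy as the last infusion day, as the Appendix VI forms do by asking when the infusion ended on that day. The statement that the loss is irrecoverable rests on a half-life of hours; the only value given is from monkeys.

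The effect is on half-life and volume under a secondary aim. The primary safety and dose-finding aims are untouched.

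**What to change.** Draw the post-infusion series once per patient, at the first end of infusion in any cycle that is followed by a planned break of at least 24 h or at which continuation is undecided. If neither occurs, draw it at a known stop. Do not repeat it once drawn. Covering any cycle matters: a rule limited to the end of Cycle 1 would still miss a patient who skips the first break and is stopped during a break after Cycle 2. State that a series cut short by an early restart counts as drawn. Decisions about breaks and stopping remain as they are.

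Align Section 8.2.2, footnote 1 of the Section 8.1 table, map codes e and p, the Appendix VI forms and Appendix II. Correct the last-day wording as well, since the 24 h sample falls on the following day (Day 30 if the infusion ends on Day 29).

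Cost: no added samples, because one series keeps the total at 10 + 6 = 16 to 13 + 6 = 19, and at most 57 ml. A series at the end of Cycle 1 plus another on the last day would need 22 to 25 samples and 22 × 2 = 44 to 25 × 3 = 75 ml, which exceeds Appendix II. Two drawbacks remain: the 24 h draw may need an outpatient visit, and the series will come from different cycles in different patients, so the PK analysis should record the cycle.
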